8.3 Recording of Adverse Events

Each AE should be recorded in standard medical terminology on the AE eCRF page. Whenever possible, the AE should be evaluated and reported as a diagnosis rather than as individual signs or symptoms. For example, cough, runny nose, sneezing, sore throat, and head congestion should be reported as 'upper respiratory infection'. If a definitive diagnosis is not possible, the individual signs and symptoms should be recorded. Dates of start (onset) and stop (recovery), action taken, and outcome will be recorded in the AE eCRF page.

An abnormal laboratory value will not be considered as an AE unless it is 1) assessed as clinically significant by the Investigator, 2) requires intervention, or 3) results in a delay, discontinuation or change in the dose of study treatment. A clinically significant abnormal laboratory value will not be considered an AE if it is determined to be related to the study condition or concomitant conditions, e.g., diabetes, of which the Investigator was previously aware and have not worsened. An abnormal laboratory value considered as an AE will be recorded on the AE page or module.

The Investigator will evaluate all AEs with regard to maximum intensity and relationship to study drug, as follows.

8.3.1 Maximum Intensity

Maximum intensity should be assigned using one of the severity grades as outlined in the NCI CTCAE v4.03; if the AE is not specifically listed in CTCAE v4.03, use the following grades:

- Grade 1: mild
- Grade 2: moderate
- Grade 3: severe/disabling
- Grade 4: life-threatening
- Grade 5: death

8.3.2 Relationship to Study Treatment

The degree of certainty with which an AE is attributed to study treatment (or alternative causes, e.g., natural history of the underlying diseases, concomitant therapy, etc.) will be determined by how well the event can be understood in terms of known pharmacology of ALRN-6924 (or agents administered in combination with ALRN-6924) and/or reaction of similar nature previously observed with ALRN-6924 or similar drugs. Each AE will be assigned one of the following five categories:

- *Unrelated*: There is not a temporal relationship to study drug administration (e.g., too early, too late, study drug not taken), or there is a reasonable causal relationship to another drug, concurrent illness, or circumstance.
- *Unlikely related*: There is a temporal relationship to study drug administration, but there is not a reasonable causal relationship between study drug and the AE (i.e., it is doubtful the AE is related to study drug); could be reasonably explained by other factors, including underlying disease, complications, concomitant drugs, or concurrent treatment.
- *Possibly related*: There is a reasonable temporal sequence from administration of the drug (e.g., occurred in a time frame relevant to administration of study drug, including the outcome after withdrawal of study medication, if applicable); or for which the possibility of the study drug being the causative factor (e.g., existence of similar reports attributed to the suspected drug and its analogues; reactions attributable to the pharmacological effect) could not be excluded, although other factors such as underlying disease, complications, concomitant drugs, or concurrent treatment are presumable.
- *Probably related*: There is a reasonable temporal sequence from administration of the drug (including the course after withdrawal of the drug); and for which the possibility of factors other than the drug, such as underlying disease, complications, concomitant drugs, or concurrent treatment, could not be excluded as the cause.
- *Definitely related*: Follows a clear temporal sequence from administration of the study drug; could not be possibly explained by the known characteristics of the patient's clinical state, environmental or toxic factors, or other modes of therapy administered to the patient; disappears or decreases on cessation or reduction in dose of the study drug; reappears or worsens when the study drug is re-administered; or follows a response pattern known to be associated with administration of the study drug.

8.4 Adverse Event Reporting

Each AE is to be reported by the Investigator as serious or non-serious according to the definitions above. This classification that determines the regulatory reporting procedures to be followed is described in Table 5.

Table 5: Reporting Guidelines for Adverse Events

Gravity of AE	Reporting Time to Sponsor	Type of Report
Serious	Within 24 hours after the site becomes aware of the event	Initial SAE Report
	Within 4 working days after the site becomes aware of the event	Completed SAE Report
Non-Serious	Per AE eCRF page	Completed AE eCRF page

Any SAE, regardless of relationship to study treatment that occurs during therapy or within 30 days after the last dose of study treatment must be reported to the Sponsor within 24 hours after the site becomes aware of the event. The Investigator is encouraged to discuss with the study Medical Monitor any adverse experiences for which the issue of reportability is unclear or questioned. The initial report should be followed by submission of a more detailed SAE Report within 4 working days of the site's knowledge of the event.

If the SAE occurs more than 30 days following administration of the last dose of study treatment, SAEs should be reported only if considered related to study treatment. In the event of patient death, the reason for death should be recorded as the SAE, with 'death' recorded as the outcome on the SAE eCRF module.

The SAE also will be recorded as an AE on the AE eCRF page. Note: the SAE Report is different from the AE eCRF page. In areas of both forms where the same data are reported, the forms will be completed in a consistent manner. For example, the same term should be used for the AE on both forms, with the same start and stop dates, action taken, outcome, etc.

An SAE Report should be prepared with as much available information concerning the event as possible so that a written report can be filed with the appropriate regulatory authorities. If causality cannot be determined definitively at the time of the SAE occurrence, it is important to notify the Sponsor within the timeline stated above, and to attribute the relationship as 'Not Assessable' (only applicable for the initial SAE Report). When new significant information is obtained and the outcome and attribution of the event is known, the Investigator will communicate this in a follow-up SAE Report. This relevant information will be provided in a timely manner to allow reporting to regulatory authorities within the required reporting period. Any SAE follow-up information requested by the Sponsor should be provided in a timely manner.

As necessary, the SAE Report should be accompanied by relevant pages from the eCRFs, e.g., medical history, AEs, concomitant medications. Additional information may be requested by Sponsor in an expedited manner to ensure that the initial reporting of the SAE made to the regulatory authorities complies with the required time frame. The Sponsor may be required to collect and report additional

information to the regulatory authorities in a follow-up report, containing a final evaluation of the event, including copies of hospital reports, autopsy reports, or other relevant information.

The Sponsor will provide information regarding SAEs and IND safety reports to Investigators for notification of IRBs in accordance with FDA regulations.

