8.1 Adverse Event Definitions

8.1.1 Adverse Event

An AE includes any noxious, pathological, or unintended change in anatomical, physiological, or metabolic functions as indicated by physical signs, symptoms, and/or laboratory changes occurring in any phase of the clinical study whether or not temporally associated with the administration of study medication and whether or not considered related to the study medication. This definition includes an exacerbation of pre-existing medical conditions or events, intercurrent illnesses, hypersensitivity reactions, drug interactions, or clinically significant laboratory findings.

An AE does not include the following:

- Medical or surgical procedures, e.g., tooth extraction, transfusion, surgery (The medical condition that leads to the procedure is to be recorded as an AE.)
- Pre-existing conditions or procedures present or detected at the start of the study that do not worsen
- Hospitalization for elective surgeries or for other situations in which an untoward medical event has not occurred
- Abnormal laboratory value, unless it is clinically significant according to the Investigator, requires intervention, or results in a delay, discontinuation or change in the dose of study drug
- Overdose of study drug or concomitant medication unaccompanied by signs/symptoms; if sign/symptoms occur, the final diagnosis should be recorded as an AE.
- Pregnancy by itself, unless a complication occurs during pregnancy leading to hospitalization; in this case, the medical condition that leads to the hospitalization is to be recorded as the AE.
- A significant worsening of the disease under investigation including death which is captured as an efficacy parameter in this study and, thus, is not recorded as an AE.

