8.1.2 Serious Adverse Event

A serious adverse event (SAE) is defined as an adverse event that results in any of the following outcomes:

- Death
- Life-threatening adverse experience (i.e., immediate risk of death from the event as it occurred; this does not include an adverse event that, had it occurred in a more serious form, might have caused death)
- Persistent or significant disability/incapacitation
- Inpatient hospitalization or prolongation of existing hospitalization

- Congenital anomaly/birth defect

Important medical events that may not result in death, be life-threatening, or require hospitalization may be considered serious when, based on medical judgment, they may jeopardize the patient or may require medical or surgical intervention to prevent one of the outcomes listed in this definition.

Hospitalizations due to the underlying disease will not be reported as an SAE unless there is reason to suspect a causal relationship with the study drug.

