8.3. ADVERSE EVENTS

Treatment-emergent adverse events (TEAEs) are defined as AEs that are newly occurring or worsening on or after the date of the first dose of ALRN-6924. Reported AE terms will be coded using MedDRA version 19.1 or later.

The number and percent of subjects, and the number of events where relevant, will be summarized by SOC and PT for the following categories of TEAEs:

- All TEAEs
- Grade 3 or higher CTCAE grade TEAEs
- Related TEAEs defined as at least possibly related, as delineated by the investigator, or missing
- Serious TEAEs

- Serious related TEAEs
- TEAEs leading to discontinuation of study drug
- TEAEs leading to death

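### Protocol 8.1.1 and 8.4 give different recording rules for a death from the disease under study on therapy or within 30 days of the last dose, so the Phase 1 fatal and serious TEAE tables can mix two definitions

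*Protocol*

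**What the plan says.** Protocol 8.1.1 ends its list of what is not an AE with "A significant worsening of the disease under investigation including death". It gives the consequence as "death which is captured as an efficacy parameter in this study and, thus, is not recorded as an AE".

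Protocol 8.1.2 makes the SAE a kind of AE: it "is defined as an adverse event that results in any of the following outcomes", and death is the first outcome listed. The section has one exemption for the underlying disease: "Hospitalizations due to the underlying disease will not be reported as an SAE unless there is reason to suspect a causal relationship". It has no matching sentence for deaths.

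Protocol 8.4 requires SAEs on therapy or within 30 days of the last dose to be reported whatever their relationship to treatment, and later ones only if related. It then states: "In the event of patient death, the reason for death should be recorded as the SAE", with death entered as the outcome. It adds: "The SAE also will be recorded as an AE on the AE eCRF page". Death from the disease under study is not excepted.

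SAP 8.3 tabulates serious TEAEs and "TEAEs leading to death" by system organ class and preferred term. Its TEAE definition depends only on timing relative to the first dose and does not mention progression or disease death. Under SAP 3.1 the plan covers Phase 1 only, and tables are produced by dose cohort within regimen, by regimen and overall.

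**The concern.** A patient who dies of the cancer within the reporting window is recorded differently depending on which protocol section the site follows. The SAP builds its fatal and serious TEAE tables from AE records and does nothing to bring the two rules together.

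Such deaths are plausible. Protocol section 4 enrols patients with advanced disease who are refractory to or intolerant of standard therapy, or who have none. Protocol 5.3 lets treatment continue past progression when the patient is benefiting. Protocol 3.3 plans 15 to 25 sites for the whole study, so differing readings are foreseeable.

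Safety is a primary objective of the dose-escalation phase and there is no control arm. The fatal and serious rates will be read at face value and compared across small dose cohorts. A difference between cohorts could reflect which section a site applied rather than the drug.

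**Working it through.** The plan states no figure to reproduce. The check sets the sections side by side and then sizes the effect of one record.

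**Step 1. Follow one death from the disease under study, inside the window.**

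| Step | Following 8.1.1 | Following 8.4 literally |
|---|---|---|
| Is it an AE? | No | Not asked; the trigger is the death |
| Is it an SAE? | No, because 8.1.2 makes an SAE a kind of AE | Yes, under the reason for death |
| Is it on the AE page? | No | Yes |
| Is it in the SAP 8.3 fatal and serious tables? | No | Yes |

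**Step 2. Fix the window.** Protocol 8.4 limits SAEs more than 30 days after the last dose to related ones. The conflict is therefore confined to deaths on therapy or within 30 days. Protocol 8.2 and 8.5 close AE reporting sooner if new anticancer therapy starts, which narrows it a little further.

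**Step 3. Size the effect of one death.**
- Inputs: about 75 dose-escalation patients (Protocol 3.3, SAP 2.2) and cohorts of three to six (Protocol 5.5.3).
- Formula: shift in the fatal-TEAE rate = 1/n, for a patient with no other fatal TEAE.
- Whole phase: 1/75 = 1.3 percentage points.
- Cohort of six: 1/6 = 16.7 points. Cohort of three: 1/3 = 33.3 points.
- The serious-TEAE rate moves by the same amount only if that patient had no other serious TEAE.
- SAP 2.2 counts the 75 without replacements, and some cohorts may be enlarged or pooled. Where n is larger, the shift is smaller.
- For k such deaths the phase-wide shift is at most k/75. The documents do not give k.

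**Step 4. See whether the death can be recovered elsewhere in the Phase 1 SAP.**
- Discontinuation reasons (SAP 6.1) include death, but without its cause. A patient who stopped for progression and then died counts under progression.
- PFS, duration of response and duration of clinical benefit (SAP 4.2) use the first of progression or death. A death after recorded progression adds nothing to them.
- The Phase 1 SAP has no overall survival endpoint.
- Protocol 7.2 accounts for patients who died, and SAP 3.1 lists all data, but no summary of deaths by cause is specified.

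**The case against.** The strongest reply is that the sections can be read together. Section 8.4 opens by classifying AEs as serious or not according to the earlier definitions. An event that 8.1.1 has removed from the AEs would then never reach 8.4. On that reading, the sentence on death only tells the site which term to enter once an SAE exists. That fits 8.3, which prefers a diagnosis to signs and symptoms. This reading is reasonable, but the protocol does not state it. The sentence is triggered by a patient's death rather than by an SAE, and where the protocol wanted an underlying-disease exemption, for hospitalizations, it wrote one.

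Central checks also help. Section 8.4 invites sites to raise doubtful reportability with the Medical Monitor, who under 8.10.2 reviews all SAEs. That can catch a disease death reported as an SAE. It is less likely to catch one that a site, following 8.1.1, never reported.

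Progression recorded as a fatal event would usually appear under its own preferred term and could be separated by eye. That lets a reader take out the deaths that were entered, but not add back those that were not.

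Three further points stand and limit the finding:
- A DLT must be at least possibly related to study drug (Protocol 5.9.2), so escalation does not turn on deaths attributed to the cancer.
- The related and serious-related TEAE tables are largely protected. The exception is that SAP 8.3 counts a missing relationship as related.
- PFS counts death from any cause and does not depend on the AE page.

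**Conclusion.** The finding holds for deaths from the disease under study during therapy or within 30 days of the last dose. For these, 8.1.1 and the literal text of 8.4 give opposite recording instructions, and the SAP does not resolve them. The Phase 1 fatal and serious TEAE tables can mix two definitions. The size is up to 1.3 percentage points per death across the planned 75 patients, and 17 to 33 points in a cohort of six to three. This assumes that the patient had no other event in the same table and that sites differ in which section they follow.

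A reader might infer more than the documents support:
- *That 8.4 pulls in every death.* Its own 30-day limit on unrelated SAEs rules this out.
- *That a total number of affected patients can be stated.* This would need a rate of early disease death, and neither document gives one.
- *That dose decisions or efficacy results are compromised.* The relatedness condition on DLTs and the any-cause definition of PFS argue against it.
- *That the Phase 2a tables are shown to be affected.* The conflicting protocol text applies to every part, but the tables named here are in a Phase 1 plan. The separate Phase 2a plan is not among the documents.

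**What to change.** Put one rule in both protocol sections. One way is to add to 8.4, after the sentence on patient death: *except deaths due solely to the disease under study, as defined in 8.1.1*. Removing the exclusion from 8.1.1 would also give a single rule; the sponsor should choose and say so.

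In SAP 8.3, add a listing and count of all deaths on treatment or within 30 days of the last dose, by cause: disease under study, adverse event, other. State how disease deaths already on the AE page are handled in the fatal and serious tables. No death is then lost, and the fatal-TEAE table has one definition.

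The cost is one protocol sentence and one extra SAP listing with its handling rule. The listing needs a recorded cause for each death. The documents do not describe where cause is held for a death kept off the AE page, so the sponsor should confirm this. If Phase 1 data are already collected, the listing and rule still help, because they show the reader how many deaths each recording rule would count.

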8.5 Adverse Event and Serious Adverse Event Follow-Up

All AEs and SAEs observed while a patient is receiving study treatment should be followed until resolution, return to baseline, or it is deemed that further recovery is unlikely. For patients who have discontinued study treatment, all AEs and SAEs that occur within 30 days after the last administration of study treatment or withdrawal from the study must be reported unless the patient starts new anticancer therapy. Any AE or SAE deemed related to study drug should be followed until resolution or stabilization, or until the patient starts new therapy. All measures required for AE management and the ultimate outcome of the AE will be recorded in the source document and eCRF.

For SAEs occurring from the patient's first administration of study treatment, during the study or within 30 days of the last administration of study drug, the Investigator should submit follow-up reports to the Sponsor regarding the status of the SAE and the patient's subsequent course. Follow-up reports should be submitted until the SAE has subsided, until the condition stabilizes (in the case of persistent impairment), the patient receives alternative therapy, or the patient dies.

8.6 Ongoing Safety Evaluation

During DEP, a study safety evaluation will be conducted on a regular (monthly) basis by teleconference, led by the Sponsor's Medical Monitor and participating Principal Investigators. All available dose exposure, dose-limiting toxicity, AE/SAE profiles and clinical laboratory abnormalities, and other safety measures will be reviewed during each convened meeting. Patient accrual will not be interrupted during the regularly scheduled safety evaluations.

The same process will be followed for the assessment of safety run-ins conducted during the EXP; however, these safety evaluations will be triggered by the accrual of a target number of safety evaluable patients, rather than occurring on a monthly basis.

8.7 Pregnancy

Any pregnancy diagnosed during the study, or that occurs within 30 days after stopping study medication, must be reported immediately to the Investigator. Pregnancy, in and of itself, is not regarded as an adverse event, unless there is suspicion that study medication may have interfered with the effectiveness of a contraceptive medication. If the patient becomes pregnant while on-study, the study drug should be immediately discontinued. Pregnancy information about a female patient or a female partner of a male patient should be reported immediately from the time the Investigator first becomes aware of a pregnancy or its outcome. This will be performed by the Investigator completing a Pregnancy Form.

Any pregnancy complication, spontaneous abortion, elective termination of a pregnancy for medical reasons, outcome of stillbirth, congenital anomaly/birth defect, or serious adverse event in the mother will be recorded as an SAE and will be reported as described in [Section 8.4](#).

8.8 Medication Errors

A medication error for this study is defined as any accidental incorrect administration of a medicinal product. The error may be related to the administration of a wrong medication, nature of the medication, route of administration, dosage or frequency of the treatment as specified in this protocol (including omission of one or more administrations).

- Medication errors with concomitant medication treatment will not be recorded in the CRF unless they result in an AE.
- Medication errors with the study medication that result in an AE will be captured as an AE in the CRF.
- Medication errors with the study medication resulting in an overdose, incorrect route of administration, or administration with the incorrect study drug will be reported to Safety Desk as soon as they are known regardless of whether or not a subsequent AE has occurred.

8.9 Overdose

An overdose with ALRN-6924 for this clinical trial is defined as an accidental or intentional overdose with ALRN-6924 regardless of whether it is associated with an AE (even if not fulfilling a seriousness criterion), and is to be reported to Safety Desk within 24 hours from the time the Investigator first becomes aware of its occurrence following the same process as described for SAEs.

There is no known antidote available in case of ALRN-6924 overdose. Overdose should be managed aggressively with close monitoring and administration of prophylactic and symptomatic therapies to prevent or correct potential side effects.

For information regarding overdose of palbociclib, refer to the current approved US prescribing information.

